## **12.8 Exposure to Study Drug**

A listing with information about the drug administration will be provided.

## **12.9 Baseline Parameters and Concomitant Medications**

Summary statistics (mean, median, standard deviation, min, max, number of available observations) will be provided for continuous demographic variables (e.g., age, height, weight). Individual patient listings of demographic data will be provided.

Qualitative demographic characteristics (gender, race) will be summarized by counts and percentages. Other baseline patient characteristics (medical history, physical examination clinical findings, previous medications, inclusion/exclusion checklist) will only be listed.

Distributions of these parameters will be compared between the treatment groups only descriptively. No statistical inference will be performed.

Previous and concomitant medications will be coded by the sponsor according to the WHO drug code and the ATC class code.

## **12.10 Exploratory Analyses**

Exploratory data-driven analyses can be performed with the caveat that any statistical inference will not have any confirmatory value.

## **12.11 PET Image Data Analysis**

PET data analysis will be performed using PET site's in-house MIAKAT™ software package. MIAKAT™ is implemented using MATLAB (The Mathworks Inc., Natick, MA, USA), and makes use of SPM (Wellcome Trust Centre for Neuroimaging, <http://www.fil.ion.ucl.ac.uk/spm>) for image segmentation and registration. MIAKAT™ implements a robust and consistent analysis pipeline with built-in audit trail and pre-specified QC points whereby the analyst is required to inspect results of intermediate stages (for example checking the success of automated corrections for subject motion or assessing the quality of model fits).

### 12.11.1 Image processing

Each subject's structural MRI image will undergo grey matter segmentation and registration to a standard reference space (MNI152, ([Grabner et al. 2006](#)). The MNI152 template brain image and associated atlas (CIC atlas, ([Tziortzi et al. 2011](#)) will be nonlinearly warped to the subject's MR image to enable automated definition of regions of interest (ROIs).

The set of ROIs to be considered and reported will be selected based on previous studies ([Paul et al. 2018](#)), and the signal observed in these human PET scans and may include (but not be limited to) the frontal, parietal and occipital lobes, insular cortex, posterior cingulate gyrus, anterior cingulate, caudate nucleus, putamen, nucleus accumbens, thalamus, amygdala, hippocampus and cerebellum.

Dynamic PET images (90-minute duration) will be generated on the PET scanners using the manufacturer's recommended reconstruction settings which include corrections for scatter, randoms and attenuation. These will then be registered to each subject's MRI scan and corrected for motion using a frame-to-frame registration process with a normalised mutual information cost function. ROIs defined on the MRI images will be applied to the dynamic PET data to derive regional time-activity curves (TACs), with activity concentrations expressed as standardised uptake values (SUV), given by:

$$SUV = \frac{Act}{IA/BW}$$

where *Act* is the measured radioactivity concentration (kBq/ml), *IA* is the injected radioactivity (MBq) and *BW* is the subject's bodyweight (kg).

### 12.11.2 Arterial blood data processing

Continuous blood data will be scaled (i.e., calibrated) to match overlapping discrete whole blood samples, and then merged with the remaining discrete whole blood data to form a whole blood activity curve covering the duration of the scan. Activity measurements from the discrete plasma samples will be divided by the corresponding whole blood data to form plasma-over-blood (POB) data. The POB data will be fitted to a simple model in order to smooth and interpolate the relationship. The POB model fit curve will be multiplied by the whole blood curve to give an estimated total plasma curve.

Parent fraction (metabolite) data will be fitted to an appropriate simple model, to be determined empirically. The resulting fitted parent fraction profile will be multiplied by the total plasma curve (calculated as described above) and then smoothed post-peak using a multi-exponential fit to give the required parent plasma input function. For each scan, a time delay will be fitted and applied to the input function to account for any delay between blood sampling measurements and tissue data from the PET tomograph. The resulting parent plasma input function will be used as input for the kinetic modelling processes described in [Section 12.11.3](#).

### **12.11.3 Signal change evaluation**

Decreases in  $V_T$  from baseline to post-dose scans will be interpreted as an effect of O-GlcNAcase occupancy by ASN51. Target occupancy estimates may be directly calculated from scan data via methods including a ‘Lassen plot’ (Cunningham et al. 2010). Alternatively, the relationship between exposure and occupancy may be explored by direct fitting of a saturation model to pooled (across subjects and scans)  $V_T$  data, to obtain for example an estimate of EC50 for occupancy by ASN51. It is anticipated that data from the first subjects will be sufficient to enable a definitive selection of an appropriate analysis method to support the fulfilment of the study objectives. Data and analysis will be explored on an ongoing basis for the first four (completing) subjects. Following analysis of data from these four subjects, the data analysed to that point will be reviewed. An updated Image Analysis Plan will then be generated if appropriate, with the intention of fixing the image analysis methodology to be used for data from subsequent subjects and the dataset as a whole.

### **12.11.4 PET Data Reporting**

The PET site [REDACTED] will produce a separate Imaging Analysis Report on the PET scans and the PET scan data. A STDM dataset of the report will be generated by the PET site. The RO values will be listed in both reports for sessions 2 and 3, respectively, together with the plasma concentration of ASN51 at the time of the start of each post-dose PET scan; which will be calculated by log-linear interpolation from the two closest pk data points by subject and treatment (data will come from the sponsor).

These concentration data will be transferred to the PET site for the PK-RO analysis. Three PK-RO analyses will be done: for session 2, for session 3 and for pooled data of session 2 and session 3.

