Statistical Considerations	
A full description of the statistical evaluations, general considerations, and procedures for handling missing data will be provided in the Statistical Analysis Plan (SAP) and, if applicable, in the data management plan (DMP). The SAP will provide full details of the analyses, the data displays and the algorithms to be used for data derivations.
 
In general, trial data will be reported using summary tables, figures, and data listings. Descriptive statistics will be used to summarize the data. For continuous variables, the mean, standard deviation, median, minimum, and maximum will be provided. For discrete data, incidence and percentages will be provided. Statistical tests will be 2-sided at the alpha level of 0.05, unless stated otherwise.
 
For the analysis of the PET data, O-GlcNAcase occupancy will be quantified for each post-dose PET scan as the fractional change from the subject's baseline PET scan. Decreases in regional total volume of distribution (<math>V_T</math>) from baseline to post-dose scans will be interpreted as an effect of O-GlcNAcase occupancy by ASN51. The Lassen plot will be used to estimate the target occupancy by calculating the changes of <math>V_T</math> between baseline and post-dose against baseline <math>V_T</math> for 14 brain regions of interest. The non-displaceable volume of distribution (<math>V_{ND}</math>) will be constrained to be equal for all scans within a subject.
 
Occupancy estimates will be plotted against plasma concentrations of ASN51, corresponding to the start of each post-dose PET scan. The following model will be fitted to the occupancy data set.
 $RO = 100 \times (C_p / (C_p + EC_{50}))$ 
Where <math>RO</math> is the estimated receptor/target occupancy (%), <math>C_p</math> is the measured plasma concentration of ASN51 (ng/mL) and <math>EC_{50}</math> is the plasma concentration of ASN51 that corresponds to 50% receptor/target occupancy.
 
Treatment-emergent AEs will be tabulated and summarized by Medical Dictionary for Regulatory Activities (MedDRA) System Organ Class (SOC) and Preferred Term (PT). The number and percentage of patients who experienced AEs coded with the same PT and SOC will be summarized by treatment group (in descending order according to the incidence in the investigational study drug
	

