## 7.0 INVESTIGATIONAL PLAN

### 7.1 Study Design

This is an open-label, adaptive-design PET study to investigate the occupancy of O-GlcNAcase by ASN51 after single oral doses in healthy adult male and female subjects (aged 25-55 years, inclusive). The study schema is depicted in [Figure 2](#).

**Figure 2:** Phase 1a ASN51-102 Study Schema

Up to 10 subjects will be enrolled. Each subject will have up to 3 imaging sessions, with one scan in each session. In the first imaging session, subjects will have 240 ml of water followed by a baseline PET scan approximately 2 h later. In the second and third imaging sessions, subjects will receive a single oral dose of ASN51 with 240 ml of water, followed by an on-treatment PET scan. Safety and pharmacokinetic data of the SAD study ASN51-101 will be assessed by the SRC prior to the dosing of the first subject(s) to determine the first dose level to be administered in session 2 after the baseline session 1 and the timing of the PET scans in relation to the study drug administration time. At most 2 subjects will be dosed on the same study day. For subsequent sessions, the dose level and the time of the PET scan in all imaging session 2 and 3 will be determined after review of the results from the first on-treatment PET scan, including the PK data. Subjects will receive an intravenous dose of the radiolabelled tracer, [F]-IMA601, at the start of each PET scan.

This study will have an adaptive design: to adequately evaluate the exposure versus receptor occupancy (RO) relationship, various doses of ASN51 of up to 85% of the highest well-tolerated dose level in the preceding SAD study ASN51-101, and the timing of on-treatment PET scans may

be altered based on emerging data or study logistical requirements. On-treatment PET scans may be scheduled up to 48 h post-dose.

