After each on-treatment PET scan, the SRC will review available RO, PK, safety and tolerability data, before selecting the dose and PET scan timings for imaging session 3. Arterial blood sampling will be done during each PET scan to quantify the parent tracer related radioactivity over the course of the PET scan, and to establish a tracer metabolite corrected plasma input function. The total arterial blood volume required for each tracer injection will not exceed 145 mL. Arterial cannulation and arterial blood sampling may be reduced or removed if analysis of PET data from previous subjects indicates that noninvasive analysis of the PET scan data can be done. If a non-invasive analysis is not possible, the use of an arterial cannula with each PET scan will continue through the study.

Subjects will be screened within 21 days before their baseline PET scan. Their on-treatment PET scans will be within 7 days of their baseline scan with an interval of 7–14 days between imaging sessions 2 and 3. Subjects will be confined for 72 h after the study drug administration in sessions 2 and 3. After the baseline scan in session 1 without study drug administration, subjects may leave the unit in the evening. In the case of a technical failure (such as unsuccessful tracer synthesis), subjects may be asked to attend an additional on-treatment imaging session, in which they will receive a third oral dose of ASN51. There will be at least 7 days between each dose of ASN51. Subjects will not have more than 3 PET scans or 3 doses of ASN51 during the study. Subjects will have a follow-up visit at the research unit 7 days ( $\pm$  3 days) after imaging session 3 (Day 8).

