## 7.8 Scientific Rationale for Study Design

ASN51 is a reversible and substrate competitive inhibitor of O-GlcNAcase that is currently being developed by Asceneuron S.A for the treatment of AD.

The primary objective of this study is to investigate the occupancy of O-GlcNAcase using PET and the O-GlcNAcase ligand [F]-IMA601, and to characterize the relationship between plasma concentration of ASN51 and the occupancy of O-GlcNAcase. These data will serve as a basis for the planning of the dosing and dosing regimen in further clinical studies.

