### 12.2 Analysis Populations

Three different analysis sets are defined. Subjects who withdraw from the study, or who have missing data, will be included in the statistical analyses provided that they are eligible for inclusion in the analysis population as described below.

**All-treated set:** This analysis set includes all randomized subjects who received study drug (at least one dose).

**Safety set:** This analysis set includes subjects from the all-treated set who had at least one safety assessment post-baseline. The safety set will be employed in the analysis of tolerability and safety variables.

**PET population:** The PET population will consist of randomised subjects who receive study medication, have a baseline PET scan, at least one post-baseline PET scan, and a PK result immediately preceding PET scan.

**PK analysis population:** The PK analysis population will consist of the subjects who provide evaluable data for the comparisons of interest. These subjects should have at least one quantifiable plasma concentration, should not have violated any major entry criterion likely to confound the PK analysis, and should not have deviated significantly from the protocol between enrolment and successful study completion

In all populations, treatment will be assigned based upon the treatment subjects actually received.

The primary endpoint will be analyzed using the PET population.

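### Does the plan need a stated method for the precision of the pooled session 2 and 3 EC50, given two linked scans per subject?

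*Protocol*

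**What the plan says.** Protocol 7.1 sets the structure: "Each subject will have up to 3 imaging sessions, with one scan in each session". The first scan is the baseline and the other two are on treatment, so a subject gives at most two occupancy values. With at most 10 subjects (12.3), the pooled data set has at most 20 points. Some subjects may give only one, because the PET population in 12.2 asks only for a baseline scan, "at least one post-baseline PET scan, and a PK result immediately preceding PET scan".

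The synopsis (Statistical Considerations) says that "O-GlcNAcase occupancy will be quantified for each post-dose PET scan as the fractional change from" the subject's own baseline scan, and that V_ND "will be constrained to be equal for all scans within a subject". It then says: "The following model will be fitted to the occupancy data set". The model is RO = 100 × Cp/(Cp + EC50), with one EC50 and no subject term or error model. Section 12.11.4 adds: "Three PK-RO analyses will be done: for session 2, for session 3 and for pooled data of session 2 and session 3".

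Section 12.11.3 leaves the occupancy method open (Lassen plot or a direct fit to pooled V_T) until four subjects have completed. It provides for an updated Image Analysis Plan to fix the methodology. SAP section 3 takes the PK-RO analysis out of the SAP's scope, and SAP 15.1 says the PET site will supply it for the study report. No passage in either document states an estimation method, standard error or confidence interval for EC50.

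**The concern.** The two values from one subject are not independent. A subject whose EC50 lies above the average has lower occupancy than the fitted curve at both scans, and any error in the shared baseline scan enters both values. A routine that counts 20 independent scans, when there are 10 subjects, overstates the information. The protocol handles the same structure explicitly elsewhere: the concentration-QT regression in 12.7 has subject as a random effect.

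The result also has a use. Of the occupancy data, protocol 7.8 says: "These data will serve as a basis for the planning of the dosing and dosing regimen in further clinical studies". Under the stated model the concentration for a fractional occupancy p is EC50 × p/(1 − p), a fixed multiple of EC50. An EC50 interval that is too narrow would therefore make every concentration read from the curve look more certain than it is.

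**Working it through.** **Inputs from the documents.** At most 10 subjects; up to two on-treatment scans each; one shared baseline scan and one V_ND per subject; a one-parameter model. The documents give no precision figure for EC50, so there is nothing to reproduce.

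**Assumed inputs.** The between-subject SD of log EC50 (τ), the scan error and the range of concentrations are not in the documents and are varied below.

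**Direction, by algebra.** Let g_ij be the slope of RO on log EC50 for subject i at scan j; it always has the same sign. Let G_i be the sum of g_ij² over the subject's scans.

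- Between-subject part of the true variance of the estimate: τ² × ΣG_i² / (ΣG_i)², which is at least τ²/n.
- Part that ordinary least squares credits with two points per subject: about τ²/(2n).

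For τ = 0.3 and n = 10 these are 0.09/10 = 0.0090 and 0.09/20 = 0.0045. Scan error alone gives an SE of 0.062 in the table below (τ = 0), a variance of 0.0038. The true SE is then at least √(0.0090 + 0.0038) = 0.113, while least squares reports about √(0.0045 + 0.0038) = 0.091. The simulated values are 0.119 and 0.086.

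**Size, simple simulation.** 10 subjects × 2 scans, residual SD 5 occupancy points, concentrations log-uniform over 0.1 to 10 × EC50, 2000 runs. The clustered SE includes the factor √(n/(n−1)), with t on n−1 df.

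| τ | True SE | Mean least-squares SE | Least-squares coverage | Clustered coverage |
|---|---|---|---|---|
| 0 | 0.062 | 0.060 | 95.0% | 94.6% |
| 0.2 | 0.091 | 0.074 | 89.1% | 94.3% |
| 0.3 | 0.119 | 0.086 | 85.7% | 92.9% |
| 0.5 | 0.175 | 0.119 | 82.9% | 94.4% |

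With τ = 0 but a shared subject error of 3 points, as a noisy baseline scan might produce, least squares covers 92 to 93% across three concentration layouts.

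**Size, full chain.** 14 regions, Lassen plot with V_ND common within subject, 6 or 10 subjects, scan-level error 5 or 10%, regional error 3%, concentrations 0.3 to 6 × EC50:

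- τ = 0.2 to 0.4: least squares 83 to 92%, clustered 94 to 95%.
- τ = 0: least squares 92 to 94%, clustered 94 to 95%.
- Single-session fits, one point per subject: 94 to 95%.
- Mean error in log EC50: −0.012 to 0.032, so the estimate is nearly unbiased.
- With 30 to 50% of subjects giving one point and τ = 0.2 to 0.4: least squares 85 to 93%, clustered 93 to 94%.
- With session 3 concentration chosen from the subject's session 2 occupancy (7.1 has the committee review occupancy "before selecting the dose and PET scan timings for imaging session 3"): least squares 82 to 92%, clustered 94 to 95%.

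As an example, with 5% scan error and τ = 0.3 the interval goes from EC50 ×/÷ 1.18 to ×/÷ 1.27 with 10 subjects, and from ×/÷ 1.24 to ×/÷ 1.40 with 6. On the log scale the width ratios are ln 1.27/ln 1.18 = 1.44 and ln 1.40/ln 1.24 = 1.56.

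If regional error dominates (scan 2%, regional 5%), least-squares coverage falls to 67 to 79%. Part of that loss is a Lassen-plot bias of about −5% in EC50, which no treatment of clustering removes, so those figures do not measure this point.

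**The case for a change.** The best case for a change is that the gap is real and cheap to close. Protocol 12.1 says the SAP will carry full details of the analyses, yet the SAP hands PK-RO to the PET site. The updated Image Analysis Plan is only conditional, and what 12.11.3 says about it concerns image methodology, not the precision of EC50. SAP 10.1 allows 95% intervals where they help interpretation. Enrolment stops once the committee considers the concentration-occupancy relation well enough characterised (12.3), which can be read as a judgement about precision. One sentence would settle the matter.

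The silence of both documents stands, and so does the direction of the error. The rest is weaker. SAP 10.1 is a general display convention in a document that excludes PK-RO. Section 12.3 leaves stopping to the committee's opinion; it could equally mean that the concentration range has been covered, and no passage gives the committee an EC50 interval. Nor is there one obvious sentence to add. A subject random effect on log EC50, a subject-level bootstrap and a clustered SE are all defensible, and details matter with so few subjects. At 6 subjects, leaving out the √(n/(n−1)) factor lowers clustered coverage to about 92 to 93%. For the direct V_T fit, which the protocol keeps open, a clustered SE covered only 91 to 94%. Fixing one rule now, before the occupancy method is chosen, would be a preference.

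**Conclusion.** No change to the plan. Carried out as written, it gives a sound pooled EC50 and two single-session estimates to set beside it, each with one point per subject. The fault would arise only if someone chose to report an interval, computed it as if scans were independent, and EC50 or a shared error varied between subjects. In that case a nominal 95% interval would cover about 83 to 92% in the full-chain base case for τ of 0.2 to 0.4. That range rests wholly on assumed variances. With τ = 0 the base-case shortfall is one to three percentage points.

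The consequence is limited. The trial is hypothesis generating (protocol 12.3), the SAP has no null hypotheses (4.3), and no decision rule uses an EC50 interval. Whoever reports a standard error or interval for the pooled fit should account for subject and give the numbers of subjects and scans. An experienced PET analyst can do this without an amendment, and the Image Analysis Plan, which could not be checked here, may already require it.

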## **12.12 Clinical Study Report**

Safety and tolerability parameters as well as PK parameters will be evaluated in a Clinical Study Report.

## **13.0 TRIAL CONDUCT AND OVERSIGHT**

### **13.1 Ethics**

The trial will be conducted in accordance with the consensus ethical principles derived from international guidelines including the Declaration of Helsinki, applicable ICH Good Clinical Practice Guidelines, and applicable local laws and regulations. Should a conflict arise, the Investigator will follow whichever law or guideline affords the greater protection to the individual subject.

The protocol, protocol amendments, ICF, IB, and other relevant documents (e.g., advertisements) must be submitted to an REC/MHRA by the Investigator and reviewed and approved by the REC/MHRA before the trial is initiated.

Protocol amendments require REC/MHRA approval before implementation of changes to the trial design, except for changes necessary to mitigate an immediate hazard to subjects.

### **13.1.1 Research Ethics Committee or Medicines Healthcare and Products Regulatory Agency**

The trial proposal will be reviewed by a recognised REC, and by the MHRA. The trial will not proceed unless the sponsor obtains from the MHRA a clinical trial authorisation, and the REC approves the trial. No subject will have a PET scan without approval from the Administration of Radioactive Advisory Committee (ARSAC). The protocol, any protocol amendments, and the associated ICFs must be reviewed and approved by the REC/MHRA prior to screening of any potential subject.

All subject recruitment information must be submitted to the REC and Sponsor or its designee for review and approval prior to implementation. REC/MHRA approval of any protocol amendments must be received before any of the changes outlined in the amendments are put into effect, except when the amendment has been enacted to protect subject safety. In such cases, the chair of the REC/MHRA should be notified immediately, and the amendment forwarded to the REC/MHRA for review and approval.

